	(Refer to NCI CTCAE applicable version in study protocol for defining the CTC grade/severity)		
 
Monitor patients for signs and symptoms of poly/myositis. Typically, muscle weakness/pain occurs in proximal muscles including upper arms, thighs, shoulders, hips, neck and back, but rarely affects the extremities including hands and fingers; also difficulty breathing and/or trouble swallowing can occur and progress rapidly. Increased general feelings of tiredness and fatigue may occur, and there can be new-onset falling, difficulty getting up from a fall, and trouble climbing stairs, standing up from a seated position, and/or reaching up.
 

			
 
If poly/myositis is suspected, a neurology consultation should be obtained early, with prompt guidance on diagnostic procedures. Myocarditis may co-occur with poly/myositis; refer to guidance under Myocarditis. Given breathing complications, refer to guidance under Pneumonitis/ILD.
 
Given possibility of an existent (but previously unknown) autoimmune disorder, consider Rheumatology consultation.
 

			
 
Consider, as necessary, discussing with the study physician.
 
Initial work-up should include clinical evaluation, creatine kinase, aldolase, LDH, BUN/creatinine, erythrocyte sedimentation rate or C-reactive protein level, urine myoglobin, and additional laboratory work-up as indicated, including a number of possible rheumatological/antibody tests (ie, consider whether a rheumatologist consultation is indicated and could guide need for rheumatoid factor, antinuclear antibody, anti-smooth muscle, antisynthetase [such as anti-Jo-1], and/or signal-recognition particle antibodies). Confirmatory testing may include electromyography, nerve conduction studies, MRI of the muscles, and/or a muscle biopsy. Consider
 

Adverse Events	Severity Grade of the Event	Dose Modifications	Toxicity Management
			Barium swallow for evaluation of dysphagia or dysphonia.
			
 
Patients should be thoroughly evaluated to rule out any alternative etiology (eg, disease progression, other medications, or infections).
 

	Grade 1	• No dose modifications.	
 
For Grade 1
 
Monitor and closely follow up in 2 to 4 days for clinical symptoms and initiate evaluation as clinically indicated.
 
Consider Neurology consult.
 
Consider, as necessary, discussing with the study physician.
 

	Grade 2	
 
Hold investigational drug(s) until resolution to Grade ≤ 1.
 
Permanently discontinue investigational drug(s) if it does not resolve to Grade ≤ 1 within 30 days or if there are signs of respiratory insufficiency.
 
	
 
For Grade 2
 
Monitor symptoms daily and consider hospitalization.
 
Obtain Neurology consult, and initiate evaluation.
 
Consider, as necessary, discussing with the study physician.
 
If clinical course is rapidly progressive (particularly if difficulty breathing and/or trouble swallowing), promptly start IV methylprednisolone 2 to 4 mg/kg/day systemic steroids along with receiving input from Neurology consultant.
 
If clinical course is not rapidly progressive, start systemic steroids (eg, prednisone 1 to 2 mg/kg/day PO or IV equivalent); if no improvement within 2 to 3 days, continue additional work up and start treatment with IV methylprednisolone 2 to 4 mg/kg/day.
 
If after start of IV methylprednisolone at 2 to 4 mg/kg/day there is no improvement within 2 to 3 days, consider starting another immunosuppressive therapy such as a TNF inhibitor (eg, infliximab at 5 mg/kg IV, may be repeated at 2 and 6 weeks after
 

Adverse Events	Severity Grade of the Event	Dose Modifications	Toxicity Management
			Caution: It is important to rule out sepsis and refer to infliximab label for general guidance before using infliximab.
	Grade 3 or 4	For Grade 3	For Grade 3 or 4
		
 
Hold investigational drug(s) until resolution to Grade ≤ 1.
 
Permanently discontinue investigational drug(s) if Grade 3 imAE does not resolve to Grade ≤ 1 within 30 days or if there are signs of respiratory insufficiency.
 
Permanently discontinue investigational drug(s) for recurrent ≥ Grade 3 myositis
 
	
 
Monitor symptoms closely; recommend hospitalization.
 
Obtain Neurology consult
 
Consider discussing with the study physician, as needed.
 
Promptly start IV methylprednisolone 2 to 4 mg/kg/day systemic steroids along with receiving input from Neurology consultant.
 
If after start of IV methylprednisolone at 2 to 4 mg/kg/day there is no improvement within 2 to 3 days, consider starting another immunosuppressive therapy such as a TNF inhibitor (eg, infliximab at 5 mg/kg IV, may be repeated at 2 and 6 weeks after initial dose at the discretion of the treating provider). Caution: It is important to rule out sepsis and refer to infliximab label for general guidance before using infliximab.
 

		For Grade 4	
 
Consider whether patient may require IV IG, plasmapheresis.
 

		Permanently discontinue	
		investigational drug(s).	

a ASCO Educational Book 2015 "Managing Immune Checkpoint Blocking Antibody Side Effects" by Michael Postow MD. b FDA Liver Guidance Document 2009 Guidance for Industry: Drug-induced Liver Injury – Premarketing Clinical Evaluation.

c NCCN Clinical Practice Guidelines in Oncology "Management of Immunotherapy-Related Toxicities" Version 1.2020 – December 2019.

AchE: Acetylcholine esterase; ACTH: adrenocorticotropic hormone; ADL: Activities of daily living; AE: Adverse event; ALP: Alkaline phosphatase test; ALT: Alanine aminotransferase; AST: Aspartate aminotransferase; BUN: Blood urea nitrogen; CK-MB: creatinine kinase isoenzyme MB; CT: Computed tomography; CTC: Common Terminology Criteria; CTCAE: Common Terminology Criteria for Adverse Events; ILD: Interstitial lung disease; imAE: immune-mediated adverse event; IG: Immunoglobulin; IV: Intravenous; GI: Gastrointestinal; LFT: Liver function tests; LLN: Lower limit of normal; MRI: Magnetic resonance imaging; NCI: National Cancer Institute; NCCN: National Comprehensive Cancer Network; PJP: *Pneumocystis jirovecii* pneumonia (formerly known as *Pneumocystis carinii* pneumonia); PO: per os (taken orally); T3: Triiodothyronine; T4: Thyroxine; TBL: Total bilirubin; TNF: Tumor necrosis factor; TSH: Thyroid-stimulating hormone; ULN: Upper limit of normal.

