#### **Dosing Criteria for Cycles** $\geq 2$

Following completion of the first treatment cycle, participants may receive additional treatment with sabestomig when the following conditions are met:

- The participant does not meet any criteria for discontinuation of IMP as listed in Section 7.1
- The participant has adequate marrow, renal, and liver function, outlined in Table 9. Note: Laboratory evaluations must be performed up to 3 days prior to initiation of each cycle of treatment; transfusion and granulocyte colony stimulating factor support is permissible.
- If the participant experiences an AE following administration of study intervention in the previous dosing cycle, the participant must not meet criteria for dose omission or permanent discontinuation and must meet retreatment guidelines as outlined in the toxicity management guidelines as defined in Appendix I.

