Immunosuppressive medications, including but not limited to, systemic corticosteroids at doses exceeding 10 mg/day of prednisone or equivalent, methotrexate, azathioprine, and tumor necrosis factor- $\alpha$ blockers.	Should not be given concomitantly or used for premedication prior to the immunotherapy infusions. The following are allowed exceptions : Premedication prior to infusion of sabestomig as outlined in Section 6.5.1. Use of immunosuppressive medications for the management of study intervention-related AEs. For $\geq$ Grade 2 IRRs after Cycle 1 Day 1 per institutional standards and at the Investigator's discretion; however, steroids should not be used as routine premedication for Grade 1 or 2 IRRs (refer to Section 6.6.8 and Toxicity Management Guidelines [Appendix 1]). Use in participants with contrast allergies. In addition, use of inhaled, topical, and intranasal corticosteroids is permitted. A temporary period of steroids will be allowed if clinically indicated and considered to be essential for the management of non-immunotherapy-related events experienced by the participant (eg, chronic obstructive pulmonary disease, radiation nausea etc.)
Herbal and natural remedies which may have immune-modulating effects.	Should not be given concomitantly.

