#### **Dosing Modification and Toxicity Management Guidelines (TMGs) for Sabestomig**

#### General Considerations Regarding Immune-Mediated Reactions

#### These guidelines are provided as a recommendation to support Investigators in the management of potential imAEs.

Immune-mediated events can occur in nearly any organ or tissue, therefore, these guidelines may not include all the possible immune-mediated reactions. Investigators are advised to take into consideration the appropriate practice guidelines and other society guidelines (eg, NCCN, ESMO) in the management of these events. Refer to the section of the table titled "Other -Immune-Mediated Reactions" for general guidance on imAEs not noted in the "Specific Immune-Mediated Reactions" section. Early identification and management of imAEs are essential to ensure safe use of the study intervention. Monitor patients closely for symptoms and signs that may be clinical manifestations of underlying imAEs. Patients with suspected imAEs should be thoroughly evaluated to rule out any alternative etiologies (eg, disease progression, concomitant medications, infections). In the absence of a clear alternative etiology, all such events should be managed as if they were immune-mediated. Institute medical management promptly, including specialty consultation as appropriate. In general, withhold investigational drug(s) for severe (Grade 3) imAEs. Permanently discontinue investigational drug(s) for life-threatening (Grade 4) imAEs, recurrent severe (Grade 3) imAEs that require systemic immunosuppressive treatment, or an inability to reduce corticosteroid dose to 10 mg or less of prednisone or equivalent per day within 12 weeks of initiating corticosteroids.

Based on the severity of the imAE, treatment with sabestomig should be withheld and corticosteroids administered. Upon improvement to Grade  $\leq 1$ , corticosteroid should be tapered over  $\geq 28$  days. More potent immunosuppressive agents such as TNF inhibitors (eg, infliximab) should be considered for events not responding to systemic steroids. Alternative immunosuppressive agents not listed in this guideline may be considered at the discretion of the Investigator based on clinical practice and relevant guidelines. With long-term steroid and other immunosuppressive use, consider need for *Pneumocystis jirovecii* pneumonia (PJP, formerly known as *Pneumocystis carinii* pneumonia) prophylaxis, gastrointestinal protection, and glucose monitoring.

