	Grade 1	No dose modifications.	For Grade 1
			
 
Monitor serum creatinine weekly and any accompanying symptoms.
 

			• If creatinine returns to baseline, resume its regular monitoring per study protocol.
			• If creatinine worsens, depending on the severity, treat as Grade 2, 3, or 4.

Adverse Events	Severity Grade of the Event	Dose Modifications	Toxicity Management
			
 
Consider symptomatic treatment, including hydration, electrolyte replacement, and diuretics.
 

	Grade 2	Hold investigational drug(s) until	For Grade 2
		

resolution to Grade ≤ 1 or baseline.

If toxicity worsens, then treat as

	
 
Consider symptomatic treatment, including hydration, electrolyte replacement, and diuretics.
 

		

Grade 3 or 4.

If toxicity improves to

	
 
Carefully monitor serum creatinine every 2 to 3 days and as clinically warranted.
 

		Grade $\leq 1$ or baseline, then resume investigational drug(s)	
 
Consult nephrologist and consider renal biopsy if clinically indicated.
 

		after completion of steroid taper.	
 
If event is persistent beyond 3 to 5 days or worsens, promptly start prednisone 1 to 2 mg/kg/day PO or IV equivalent.
 

			
 
If event is not responsive within 3 to 5 days or worsens despite prednisone at 1 to 2 mg/kg/day PO or IV equivalent, consider additional workup. When event returns to baseline, resume investigational drug(s) and routine serum creatinine monitoring per study protocol.
 

	Grade 3 or 4	Permanently discontinue	For Grade 3 or 4
		investigational drug(s).	
 
Carefully monitor serum creatinine daily.
 

			
 
Consult nephrologist and consider renal biopsy if clinically indicated.
 

			
 
Promptly start prednisone 1 to 2 mg/kg/day PO or IV equivalent.
 

			
 
If event is not responsive within 3 to 5 days or worsens despite prednisone at 1 to 2 mg/kg/day PO or IV equivalent, consider additional workup and prompt treatment with an immunosuppressant in consultation with a nephrologist.
 

Rash or Dermatitis	Any Grade	General Guidance	For Any Grade
	(Refer to NCI CTCAE applicable		
 
Monitor for signs and symptoms of dermatitis (rash and pruritus).
 

	version in study protocol for		1 /

Adverse Events	Severity Grade of the Event	Dose Modifications	Toxicity Management

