	Grade 2, 3, or 4	For Grade 2, 3, or 4 In consultation with relevant pancreatic specialist consider continuing investigational drug(s) if no clinical/radiologic evidence of pancreatitis ± improvement in	
 
abdominal CT with contrast, MRCP if clinical suspicion of pancreatitis and no radiologic evidence on CT).
 
If isolated elevation of enzymes without evidence of pancreatitis, continue immunotherapy. Consider other causes of elevated amylase/lipase.
 
If evidence of pancreatitis, manage according to pancreatitis recommendations.
 

Acute Pancreatitis	Any Grade	amylase/lipase.	For Any Grade
	Any Orace	Sentral Subtance	
 
Consider Gastroenterology referral.
 

Adverse Events	Severity Grade of the Event	Dose Modifications	Toxicity Management
	(Refer to NCI CTCAE applicable version in study protocol for defining the CTC grade/severity)		
	Grade 1	No dose modifications.	For Grade 1
			– IV hydration.
			
 
Manage as per amylase/lipase increased (asymptomatic).
 

	Grade 2, 3, or 4	For Grade 2 Hold investigational drug(s) until resolution to Grade $\leq 1$ . For Grade 3 or 4 Permanently discontinue investigational drug(s).	
 
For Grade 2, 3, or 4
 
Promptly start systemic steroids prednisone 1 to 2 mg/kg/day PO or IV equivalent.
 
IV hydration.
 

Neurotoxicity	Any Grade	General Guidance	For Any Grade
(to include but not limited to non-infectious meningitis, non- infectious encephalitis, and autonomic neuropathy, excluding Mvasthenia Gravis	(Depending on the type of neurotoxicity, refer to NCI CTCAE applicable version in study protocol for defining the CTC grade/severity)		
 
Patients should be evaluated to rule out any alternative etiology (eg, disease progression, infections, metabolic syndromes, or medications).
 
Monitor patient for general symptoms (headache, nausea, vertigo, behavior change, or weakness).
 
Consider appropriate diagnostic testing
 

and Guillain-Barre)			(eg, electromyogram and nerve conduction investigations).
			
 
Perform symptomatic treatment with neurological consult as appropriate.
 

			- FOR TRANSVERSE MYELITIS OR
			MENINGOENCEPHALITIS, PERMANENTLY
			DISCONTINUE INVESTIGATIONAL DRUG(S)
			FOR ANY GRADE.

Adverse Events	Severity Grade of the Event	Dose Modifications	Toxicity Management
	Grade 1	No dose modifications.	For Grade 1 - See "Any Grade" recommendations above.

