#### Management of immune-mediated liver injury caused by immune checkpoint inhibitors (ILICI)

Recommended management of treatment-emergent abnormal hepatic biochemical tests in clinical trials with sabestomig (patients with normal baseline ALT, ASTa)

Treatment Emergent ALT/AST	TBL b Values at Time of Treatment Emergent ALT Elevation	Investigational drugs treatment adjustment and additional therapy	Monitoring and evaluation
Normal	Isolated total blood bilirubin elevation > 3 × ULN	Discontinue investigational drug.	Repeat blood tests d within 2 to 3 days. Initiate close monitoring and evaluation e .
$\leq$ 3 x ULN	Normal. Patients with Gilbert's syndrome: No change in baseline TBL.	Continue treatment.	Repeat blood tests c within 1 to 2 weeks.
> 3 x ULN	Normal. Patients with Gilbert's syndrome: No change in baseline TBL.	Withhold investigational drug. If rising ALT/AST when re-checked, start prednisone/prednisolone 1 mg/kg/d f . If ALT/AST improve to $\leq 3.0$ x ULN, resume treatment after completion of steroid taper to equivalent of prednisone $\leq 10$ mg/day.	Repeat blood tests d within 2 to5 days. Initiate close monitoring and evaluation e .
	TBL $\geq 2 \times ULN$ . Patients with Gilbert's syndrome: Doubling of direct bilirubin.	Discontinue investigational drug. Start prednisone/prednisolone 1 to 2 mg/kg/d f .	Repeat blood tests d within 2 to 3 days. Initiate close monitoring and evaluation e .
> 5 x ULN	Normal. Patients with Gilbert's syndrome: No change in baseline TBL.	Withhold investigational drug. Start prednisone/prednisolone 1 to 2 mg/kg/d f . Resume treatment if elevations downgrade to AST and ALT $\leq 3.0$ x ULN within 14 days, and after completion of steroid taper to equivalent of prednisone $\leq 10$ mg/day. Otherwise discontinue investigational drug permanently.	Repeat blood tests d within 2 to 3 days. Initiate close monitoring and evaluation e . Treatment shall only resume following consultation with a hepatologist and based on a benefit/risk assessment for the affected participant.
> 10 x ULN	Normal or elevated.	Discontinue investigational drug. Start prednisone/prednisolone 1 to 2 mg/kg/d g .	Repeat blood tests d within 2 to 3 days. Initiate close monitoring and evaluation e .

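### The Grade 2 nephritis row of Appendix I gives two resume instructions that differ on both the steroid taper and the recovery threshold

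*Protocol*

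**What the plan says.** The row is in Protocol Appendix I, Specific Immune-Mediated Reactions, under nephritis or renal dysfunction, Grade 2.

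- **Dose Modifications column.** Drug is held. It restarts once the toxicity has improved to Grade 1 or lower, or to baseline, and "after completion of steroid taper".
- **Toxicity Management column.** Prednisone at 1 to 2 mg/kg/day starts if the event persists beyond 3 to 5 days or worsens. The next bullet covers events that do not respond within 3 to 5 days, or that worsen, despite that dose. It asks the site to consider further work-up and ends: "When event returns to baseline, resume investigational drug(s) and routine serum creatinine monitoring per study protocol".

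Four other places bear on how the row is read.

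- Appendix I, General Considerations: on improvement to Grade 1 or lower, "corticosteroid should be tapered over" at least 28 days. The same section calls the guidelines a recommendation.
- Section 6.1.2, dosing criteria for Cycle 2 onwards: after an adverse event in the previous cycle, the participant "must meet retreatment guidelines as outlined in the toxicity management guidelines as defined in Appendix I".
- Table 12, prohibited medications: the limit on immunosuppressants has an exception for "Use of immunosuppressive medications for the management of study intervention-related AEs".
- The Grade 1 nephritis row has a similar sentence that deals with monitoring only: "If creatinine returns to baseline, resume its regular monitoring per study protocol".

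**The concern.** The two columns answer the same question, when drug may restart, and their answers differ. The bullet omits the taper condition for participants who, by its own terms, are already on systemic steroids. It is an affirmative instruction to resume, and no text says which column governs if they diverge.

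At stake is consistent re-dosing after a steroid-treated renal event. A site that follows the bullet alone could give sabestomig while the participant is still tapering, which the adjacent cell does not allow. Another site following the Dose Modifications cell would wait. For a participant whose creatinine improves but stays above baseline, the two sites could differ in the opposite direction. The rule stays in force in the post-trial access phase, because Section 6.9 keeps the protocol's dose-modification criteria there.

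**Working it through.** The plan gives no figure to reproduce. The check compares the two instructions and looks for any other rule that would reconcile them.

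**1. The two instructions side by side**

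| | Dose Modifications | Toxicity Management bullet |
|---|---|---|
| Recovery needed | Grade 1 or lower, or baseline | Baseline only |
| Steroid condition | Taper completed | None stated |

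**2. Earliest restart under each.** Let *g* be the day the event reaches Grade 1 or lower, *b* the day it reaches baseline, and *d* = *b* − *g*. Assume the taper starts on day *g* and lasts *T* days. General Considerations gives *T* ≥ 28.

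- Dose Modifications: *g* + *T*
- Bullet read alone: *b* = *g* + *d*
- Gap: (*g* + *T*) − (*g* + *d*) = *T* − *d*

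With *T* = 28, and values of *d* chosen only for illustration:

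| *d* (days) | Gap 28 − *d* | Bullet relative to Dose Modifications |
|---|---|---|
| 0 | 28 | 28 days earlier |
| 7 | 21 | 21 days earlier |
| 14 | 14 | 14 days earlier |
| 21 | 7 | 7 days earlier |
| 28 | 0 | same day |
| 35 | −7 | 7 days later |
| baseline never reached | – | bullet never triggers restart |

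The bullet is therefore looser when baseline comes before the taper ends, and stricter when baseline comes later or not at all.

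**3. Would a dosing date fall in the gap?** Dosing is every 21 days, and 28 / 21 = 1.33, so a full taper spans at least one nominal dosing date. This is nominal only, because drug is on hold.

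**4. Does another rule supply the missing condition?**

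- Section 6.1.2 requires the Appendix I retreatment guidelines to be met, but names no column and adds no steroid limit. It also requires adequate renal function per Table 9 (creatinine clearance of at least 45 mL/minute), which does not address steroids.
- The Table 12 exception means its limit on steroids does not block dosing during a taper given for a drug-related event.
- General Considerations calls for permanent discontinuation if steroids cannot be brought to 10 mg/day or less of prednisone within 12 weeks. That is a stopping rule and does not say when to resume.

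**5. Comparison with neighbouring rows.** Grade 2 colitis and Grade 2 rash state the resume rule once, under Dose Modifications, with the taper condition. Their Toxicity Management cells give no resume instruction.

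**The case against.** The strongest reply is that silence is not permission. The bullet does not mention the taper, so it does not authorise dosing during one, and both cells can be satisfied by waiting. The column headings already separate dosing from management, and Section 6.1.2 does not let a site pick one guideline and ignore another. Re-dosing during the taper would mean overlooking the adjacent cell. All of this stands. It limits the consequence to a site that acts on the bullet alone, but does not remove the discrepancy: the bullet is itself a dosing instruction, and its recovery threshold also differs.

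A reader might infer more than the documents support:

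- **That Appendix I permits re-dosing on high-dose steroids.** The whole row read under Section 6.1.2 points to waiting. Setting the 1 to 2 mg/kg/day starting dose against the 10 mg/day level in the liver tables does not measure the problem, because the former applies before the taper. The dose on the day of re-dosing cannot be derived.
- **That dosing during a taper is shown to be unsafe.** It is not, and Appendix I is not uniform. Grade 2 pancreatitis says only "For Grade 2 Hold investigational drug(s) until resolution to Grade" 1 or lower, and Grade 2 neurotoxicity and myositis also state no taper condition. The liver tables let sites "resume treatment after completion of steroid taper to equivalent of prednisone" 10 mg/day or less.
- **That the bullet is simply the looser rule.** Its baseline-only threshold is stricter when creatinine settles at Grade 1 above baseline.

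**Conclusion.** The point holds as an internal inconsistency in one row. The two resume instructions differ on the steroid condition and on the recovery threshold. Read alone, the bullet allows restart up to 28 days earlier than the Dose Modifications cell under a minimum-length taper. It is later, or never triggers restart, when baseline is reached after the taper or not at all.

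This rests on three assumptions: the taper starts on the day Grade 1 or lower is reached; it lasts the stated minimum (a longer taper widens the early gap); and the resume sentence applies to the events described in its own bullet. How often such events occur, and how often a site would act on the bullet alone, cannot be derived from the documents.

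Severity is minor. It is a wording correction to a safety dosing rule, within guidelines that describe themselves as a recommendation. It affects no endpoint, analysis set, sample size or decision rule.

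**What to change.** Split the sentence so that monitoring and dosing are separate, keep the baseline condition and add the taper condition. For example: *Routine serum creatinine monitoring restarts once the event is back at baseline. Sabestomig restarts only when the event is back at baseline and the steroid taper is complete.*

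Keeping baseline matters. Replacing the sentence with a bare pointer to Dose Modifications would relax recovery to Grade 1 for events that did not respond to steroids. If the sponsor intends Grade 1 or lower to suffice for these events too, the bullet should say so explicitly and then refer to Dose Modifications. The choice has a consequence: Section 6.7 calls for permanent discontinuation when treatment-related toxicity keeps sabestomig from being given for more than 12 weeks. Under a baseline-only rule, a participant who settles at Grade 1 above baseline would reach that limit.

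The cost is one bullet in the next update of Appendix I, which is already maintained as a separately dated document. No visits, procedures or analyses change.
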